Intervention Effects. Intervention effects will be assessed using linear mixed models (LMM) and generalized linear mixed models (GLMM) for continuous and categorical outcomes, respectively¹³². All hypothesis tests will be two-sided at level $\alpha=0.05$. The key outcome will be ACQ⁶³⁻⁶⁵ score; secondary measures will be examined to inform the future RCT. Separate models will be fitted for different outcome measures. If y_{ijt} is the outcome for patient j of provider i at time t , without loss generality then the following LMM will be used: $y_{ijt}=\beta_0+\beta_1*Group+\beta_2*t+\beta_3*INT+\beta_4*X_{ij}+\mu_i+\mu_{ij}+\epsilon_{ijt}$, where group, t , and INT are design variables. Group is an indicator for intervention arm and INT is an indicator for pre- or post-intervention. X_{ij} is a vector of possible PCP- and patient-level covariates. The random term $\mu_i \sim N(0, \sigma_1^2)$ is a PCP-specific random effect and $\mu_{ij} \sim N(0, \sigma_2^2)$ is a patient-specific random effect; $\epsilon_{ijt} \sim N(0, \sigma_\epsilon^2)$ is the model random error. To examine the effect of intervention on the outcome, we will conduct hypothesis test of $H_0: \beta_3=0$. We will explore differential intervention effect by sex (early adolescent and/or caregiver) and conduct exploratory analyses to determine if seasonality or differences in disease severity¹⁰⁸ between groups provide alternative explanations for findings.

Power & Sample Size. With a sample size of 10 dyads/PCP and 4 PCPs in each intervention arm (total n=10*4*2=80), and 20% attrition, we calculated the power to test the effect of intervention on ACQ. Power calculations were based on: (1) 4 repeated observations over the 3-month follow-up with a correlation of $\rho=0.8$ between repeated measures; (2) intra-cluster correlation among PCPs=0.2 to

account for clustering of patients from the same PCP; and (3) LMMs to estimate pre- and post-intervention differences. We estimated an 80% power to detect a small effect size ($d=0.15$). For ACQ, this is equivalent to detect a post-intervention difference of 0.15 (assuming $SD=0.9$).

Qualitative Data. Two or three coders will independently perform conventional content analysis¹³³. To enhance rigor, we will use multiple data sources (credibility), rich contextual descriptions (transferability), codebook and saturation tables (dependability) and audit trail (confirmability)¹³⁴⁻¹³⁷. NVivo 12 will manage data.

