9.2 SAMPLE SIZE DETERMINATION

Power & Sample Size. With a sample size of 10 patients/PCP and 4 PCPs in each intervention arm (total $n=10*4*2=80$), and 20% attrition, we calculated the power to test the effect of intervention on outcomes. Power calculations were based on: (1) 4 repeated observations over the 3-month follow-up with a correlation of $p=0.8$ between repeated measures; (2) intra-cluster correlation among PCPs=0.2 to account for clustering of patients from the same PCP; and (3) LMMs to estimate pre- and post-intervention differences. We estimated an 80% power to detect a small effect size ($d=0.15$). For ACQ, this is equivalent to detect a post-intervention difference of 0.15 (assuming $SD=0.9$).

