9.4.2 ANALYSIS OF THE PRIMARY AND SECONDARY ENDPOINT(S)

Analytic Plan.

Aims 1 & 2: Development and Intervention Feasibility. We will document our success in meeting recruitment and randomization goals, as well as process (recruitment outreach and numbers meeting eligibility criteria who accept or decline enrollment) and implementation assessments (retention rates, data completion rates, as well as fidelity, contamination and masking in the clinical trial arm).

Randomization. This is a group-randomized trial in which the primary care providers (PCPs) will be randomized within sites to the active and control conditions. We will utilize a stratified block randomization plan, stratifying by provider type (physician vs. nurse practitioner/physician assistant), to insure equal numbers of PCPs within each PCP type are assigned to each condition. Randomization lists will be computer-generated in advance by our biostatistician. Outcomes will be analyzed at the level of the early adolescent and/or caregiver.

Masking. Participants and data collectors will be masked to study hypotheses and group assignment; the investigators will be blinded to group assignment. PCPs in both intervention conditions will use tablets as part of their respective interventions and have sessions audio-recorded, facilitating masking of participants and data collectors.

Aim 3: Intervention Effects. Intervention effects will be assessed using linear mixed models (LMM) or generalized linear mixed models (GLMM) for continuous and categorical outcomes, respectively. All hypothesis tests will be two-sided at level $\alpha=0.05$. The key outcome will be ACQ score; secondary measures will be examined to inform the future RCT. Separate models will be fitted for different outcome measures. If y_{ijt} is the outcome for patient j of provider i at time t , without loss generality then the following LMM will be used:

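### The stated detectable ACQ difference of 0.15 points does not follow from d=0.15 at SD 0.9 (which gives 0.135), and the SD behind the conversion is not defined

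*Combined protocol and SAP*

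**What the plan says.** The sample size paragraph appears twice, in section 4.1 (Power & Sample Size) and in section 9.2. Both take as given 8 PCPs, 4 per arm, with 10 patients or dyads each, 80 in total. Both allow for 20% attrition and assume four repeated observations correlated at 0.8 and an intra-cluster correlation of 0.2. Section 9.2 then says "We estimated an 80% power to detect a small effect size", gives that effect as d=0.15, and continues that for the ACQ "this is equivalent to detect a post-intervention difference of 0.15", assuming an SD of 0.9. Section 4.1 has the same sentence: "For ACQ, this is equivalent to detect a post-intervention difference of 0.15".

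These two paragraphs are the only places where the plan gives a detectable effect on its primary outcome in ACQ points. Neither says whether 0.9 is a total, within-PCP, residual or change SD, and no other section gives an SD for the ACQ.

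**The concern.** A standardised effect becomes a raw one when multiplied by the SD that was used to standardise it. At SD 0.9 the raw figure must be smaller than d, yet the plan prints the same number for both. One power statement is therefore attached to two effects that differ by 11%.

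What is at stake is the target on the scale that readers will use. The ACQ is the primary outcome, and the plan says its results are to inform a future RCT, so the planning effect may be reused. If power is later recalculated and a new d obtained, that d will also have to be turned into ACQ points, and the plan as written does not show a sound conversion or say which SD belongs in it.

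**Working it through.** **Inputs** (sections 4.1 and 9.2): d = 0.15; raw difference = 0.15 points; SD = 0.9; power 80%; 40 per arm, or 32 after 20% attrition; 8 patients per PCP after attrition; ICC 0.2; correlation 0.8. Section 9.4.2 sets two-sided tests at 0.05.

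**1. The plan's conversion.** Difference = d × SD = 0.15 × 0.9 = 0.135, not 0.15. In reverse, d = difference/SD = 0.15/0.9 = 0.167, not 0.15. SD needed for both to hold: 0.15/0.15 = 1.0. Size of the gap: 0.150 − 0.135 = 0.015 points; 0.150/0.135 = 1.11.

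**2. Rounding.**
- d rounded (0.145 to 0.155): difference 0.131 to 0.140.
- Difference rounded (0.145 to 0.155): d 0.161 to 0.172.
- SD rounded (up to 0.95): difference at most 0.15 × 0.95 = 0.1425.
- All three rounded favourably: the figures can meet, but only with an SD of at least 0.145/0.155 = 0.935.

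**3. An SD definition that would reconcile the figures.** If 0.9 is a within-PCP SD and d is standardised by the total SD, then total SD = 0.9/√(1 − 0.2) = 1.006, and 0.15 × 1.006 = 0.151 points. This uses only the plan's own ICC, but the plan does not say it.

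**4. Conditional effect on power.** With z(0.975) + z(0.80) = 2.80 and all else equal:
- If 80% is right at d=0.15, power at d=0.167 is Φ(2.80/0.9 − 1.96) = 87.6%.
- If 80% is right at d=0.167, power at d=0.15 is Φ(2.80 × 0.9 − 1.96) = 71.3%.

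**5. Is the 80% right at either effect?** Normal approximation, d in total-SD units, 32 per arm. Variance components as shares of the total: PCP 0.2, patient 0.6, error 0.2.

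| Between-arm comparison | SE | Power, d=0.15 | Power, d=0.167 | d at 80% |
|---|---|---|---|---|
| Single measure, no clustering: √(2/32) | 0.250 | 8.7% | 9.8% | 0.70 |
| Mean of four measures, clustered: √[2(0.2/4 + 0.65/32)] | 0.375 | 5.9% | 6.5% | 1.05 |
| Difference in change, 1 pre and 3 post, PCP effect cancelling: √[2 × 0.2(1 + 1/3)/32] | 0.129 | 21% | 25% | 0.36 |
| ANCOVA on mean of 3 post, no clustering: √[2(0.8 + 0.2/3 − 0.64)/32] | 0.119 | 24% | 29% | 0.33 |

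Power in each row is Φ(d/SE − 1.96). In the mean-of-four row, 0.65 = 0.6 + 0.2/4. With 40 per arm, the last two rows rise only to 25% and 29% at d=0.15, and to 30% and 35% at d=0.167.

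Only variances that do not fit a clustered two-arm comparison come near 80%. One is within-patient error divided by four with no clustering (76.5% and 84.6%, 32 per arm). Another is a pre/post change pooled over both arms (64% and 73% with 32 per arm; 74% and 82% with 40).

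**The case against.** The strongest reply is that nothing depends on this figure. The paragraph attaches the 80% to d=0.15 and only then translates it, so the natural reading is that d was the quantity computed and the ACQ figure is a gloss. On that reading the printed 0.15 points errs on the conservative side, since 0.135 would be detectable. The 80 participants enter as a given and are not solved from either effect, so no enrolment number, analysis or decision rule would change. All of this stands.

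It is also fair to say that the figures may reflect an unstated definition rather than a slip. A within-PCP SD of 0.9 reconciles them almost exactly, and rounding of all three values could as well. This stands as a possibility. But the text gives the SD without qualification, so the reader cannot recover that reading, and rounding any one of the three values alone does not close the gap. Either way the passage needs a correction or a definition.

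A reader might infer more: that power at the ACQ target is really 71% or 88%, or that the trial is mis-sized by a factor of (1/0.9)² = 1.23. The documents support neither. Both power figures presuppose that 80% is right at one of the two effects, and the stated inputs give 80% at neither. The sample size factor has no consequence because the sample size was fixed in advance.

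**Conclusion.** The point holds as an inconsistency in the plan's only raw-scale detectable effect for the primary outcome. At a total SD of 0.9, d=0.15 is 0.135 points and 0.15 points is d=0.167; the printed pair needs a standardising SD of about 1.0. The gap is 0.015 ACQ points, or 11%, and does not touch the conduct of the trial. The movement of about 8 to 9 percentage points around 80% is conditional, for the reason given above.

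It would be wrong to conclude that correcting the conversion makes the power statement sound. In the between-arm variants checked, with 32 per arm, power is about 6% to 29% across the two effects and the d detectable at 80% is about 0.33 to 1.05. Those results rest on a normal approximation, on reading 0.8 as the total correlation between a patient's repeated measures, and, for the change comparison, on no PCP-by-time variation. It would equally be wrong to call the conversion a proven slip, because the SD is undefined and one definition would reconcile the figures.

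**What to change.** In both section 4.1 and section 9.2:

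1. State which SD the 0.9 is: total, within-PCP, residual or change.
2. Name one target effect and convert it with that SD. At a total SD of 0.9, write either d=0.15 with 0.135 points, or 0.15 points with d=0.167. If 0.9 is a within-PCP SD, say so and show the step through the ICC of 0.2 to a total SD of 1.006, which gives about 0.15 points.
3. In the same edit, restate the power, or the effect detectable at 80%, from the stated ICC, correlation and attrition for the between-arm contrast to be tested, and apply the same conversion to the result. For example, a detectable d of 0.33 to 1.05 is 0.33 × 0.9 = 0.30 to 1.05 × 0.9 = 0.95 points at a total SD of 0.9.

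Step 3 belongs with the first two, because printing 0.135 beside an unchanged 80% would leave an unsupported power statement with a smaller effect attached to it. The cost is a few sentences in two paragraphs and one recalculation; recruitment, procedures and data collection are unaffected.

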9.3 POPULATIONS FOR ANALYSES

INTENTION-TO-TREAT (ITT) ANALYSIS POPULATION (i.e., all randomized participants)

QUALITATIVE ANALYSIS AND RIGOR. Analysis of Qualitative Data. Guided by Qualitative Descriptive methodologies, 2-3 coders working independently of each other will systematically read the focus group transcripts to identify codes and categories using conventional inductive content analysis. An iterative codebook will be developed, and a data saturation table will be created and maintained in tandem with updates to the codebook. Data saturation, a measure of data adequacy, will signal the end of data collection (focus groups) and analysis. The creation of saturation data tables adds transparency to the process. Saturation can be reached with a small number of focus groups when the scope of the project is narrow and there is sample homogeneity (e.g., minority dyads from the same community), as in this proposal.

Directed content analysis will be used to summarize satisfaction at post-trial interviews using constructs from the Theoretical Framework of Acceptability (e.g., burden, user experience, attitudes towards the intervention and intention to participate).

Various methods of enhancing the rigor of qualitative methods will be used. Credibility will be enhanced by having disagreements about codes reconciled by consensus and by returning our findings to a small group of participants who will perform a “member check” to determine if the categories resonate with them. We will also use triangulation, a method in which multiple data sources (e.g., dyads, primary care providers) describe their perspectives. Investigators with disparate expertise (e.g., nurse scientists, public health and behavioral scientists) will serve as coders and have collaborated on the design of the trial, providing additional triangulation. Our purposive sample fosters transferability, the ability to translate findings to similar communities. Dependability and confirmability criteria will be met by the creation of an audit trail documenting data collection and analysis decisions. NVivo 12 will be used to manage qualitative data

9.4 STATISTICAL ANALYSES

9.4.1 GENERAL APPROACH

Participants will be described with respect to baseline characteristics (e.g., means, standard deviations, ranges, etc.) Descriptive data analysis will precede formal hypothesis testing to understand the data distribution and to check for outliers to determine the need for transformations of variables or special analytic techniques. We will also examine the patterns of missing data paying special attention to the balance of missing data in the study arms; linear and generalized linear mixed models provide unbiased estimates for data with missing at random when likelihood of missing is not related to the missing data and can be fully accounted for by variables where there is complete information. Intention-to-treat analyses will be conducted which requires data to be analyzed as randomized, regardless of whether participants completed some or none of the intervention. Based on our feasibility trial and the high retention rate in our previous trials, we anticipate 90% will provide baseline, 1-, 2-, and 3-month data.

9.4.2 ANALYSIS OF THE PRIMARY AND SECONDARY ENDPOINT(S)

Analytic Plan.

Aims 1 & 2: Development and Intervention Feasibility. We will document our success in meeting recruitment and randomization goals, as well as process (recruitment outreach and numbers meeting eligibility criteria who accept or decline enrollment) and implementation assessments (retention rates, data completion rates, as well as fidelity, contamination and masking in the clinical trial arm).

Randomization. This is a group-randomized trial in which the primary care providers (PCPs) will be randomized within sites to the active and control conditions. We will utilize a stratified block randomization plan, stratifying by provider type (physician vs. nurse practitioner/physician assistant), to insure equal numbers of PCPs within each PCP type are assigned to each condition. Randomization lists will be computer-generated in advance by our biostatistician. Outcomes will be analyzed at the level of the early adolescent and/or caregiver.

Masking. Participants and data collectors will be masked to study hypotheses and group assignment; the investigators will be blinded to group assignment. PCPs in both intervention conditions will use tablets as part of their respective interventions and have sessions audio-recorded, facilitating masking of participants and data collectors.

Aim 3: Intervention Effects. Intervention effects will be assessed using linear mixed models (LMM) or generalized linear mixed models (GLMM) for continuous and categorical outcomes, respectively. All hypothesis tests will be two-sided at level $\alpha=0.05$. The key outcome will be ACQ score; secondary measures will be examined to inform the future RCT. Separate models will be fitted for different outcome measures. If y_{ijt} is the outcome for patient j of provider i at time t , without loss generality then the following LMM will be used:

$y_{ijt} = \beta_0 + \beta_1 * \text{Group} + \beta_2 * t + \beta_3 * \text{INT} + \beta_4 * X_{ij} + \mu_i + \mu_{ij} + \varepsilon_{ijt}$, where group, t , and INT are design variables. Group is an indicator for intervention arm and INT is an indicator for pre- or post-intervention. X_{ij} is a vector of possible PCP- and patient-level covariates. The random term $\mu_i \sim \text{N}(0, \sigma_1^2)$ is a PCP-specific random effect and $\mu_{ij} \sim \text{N}(0, \sigma_2^2)$ is a patient-specific random effect; $\varepsilon_{ijt} \sim \text{N}(0, \sigma_\varepsilon^2)$ is the model random error. To examine the effect of intervention on the outcome, we will conduct hypothesis test of $H_0: \beta_3 = 0$. We will explore differential intervention effect by sex.

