1 PROTOCOL SUMMARY

1.1 SYNOPSIS

Title: **The Development and Pilot Testing of a Caregiver-Child Shared Decision-Making Intervention to Improve Asthma in Urban Youth**

Grant Number: **1R21NR019668**

Study Description: This is a feasibility trial of a brief shared decision-making intervention that primary care providers will deliver to caregivers and their children aged 10-14 during a routine office visit, focusing on improving self-management. Brief shared decision-making will be compared to a dose-matched attention control; providers will be randomized to deliver either the active (n = 43) or control (n = 42) intervention to dyads (N = 85) who will be followed for 3-months. The trial will be informed by focus groups (caregivers separately (n = 20) ; early adolescents separately n = 20) and dyads (n = 20) (N=60).

Objectives:

1. **To develop BREATHE-PEDS in a pediatric population (dyads of caregivers and their 10- to 14-year-old early adolescents with uncontrolled asthma) receiving asthma care in FQHCs;**
2. **To evaluate the feasibility and acceptability of intervention procedures; and**
3. **To assess intervention effects on asthma outcomes (monthly x 3 months post-intervention).**

To accomplish these aims the proposed study includes two phases: (1) a development phase where we will develop **BREATHE-PEDS** using focus groups. Participants (N = 60) will include early adolescents (n = 20), caregivers (n = 20) and dyads (n=10 dyads) to adapt **BREATHE-PEDS**, and (2) a pilot validation phase where we will conduct a group-randomized trial in two FQHCs with 85 dyads treated by 8 PCPs (10 dyads/PCP) randomized to 1 of 2 study arms: (a) **BREATHE-PEDS** (n=42 dyads), or (b) dose-matched attention control (n=43 dyads). We will conduct post-trial interviews with PCPs, caregivers, and their children to evaluate satisfaction with the intervention; we will follow caregiver-child dyads for 3 months post-intervention to assess the impact of **BREATHE-PEDS** on asthma outcomes.

Hypotheses:

1. The intervention will be feasible and acceptable as evidenced by: high rates of dyad recruitment and retention; PCP fidelity to the intervention protocol; and PCP and caregiver-child dyad satisfaction.

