6.3 MEASURES TO MINIMIZE BIAS: RANDOMIZATION AND BLINDING

DESCRIPTION OF RANDOMIZATION PROCEDURES: Prior to trial initiation, all eligible clinicians will be randomized equally into the BREATHE and the attention control condition stratified for provider type, using a computer-generated randomization list. We will obtain informed consent from the first eight clinicians on the randomization list: four/site; two physicians and two nurse practitioners [NPs]

randomized to BREATHE; two physicians and two NPs randomized to control. Those remaining on the list will be placed on “standby” if replacement is needed.

CONTAMINATION.

Contamination will be minimized by (1) training only **BREATHE-PEDS** clinicians to deliver the active intervention and (2) encouraging confidentiality regarding training and intervention content.

MASKING.

Dyads, data collectors, and the statistician will be blinded to assignment. Consent materials will inform dyads that the focus of the trial is on the communication they have with their clinician about asthma management and control. Immediately after the intervention, dyads will be asked to guess the condition to which their clinician had been randomized. At the end of participants’ final data collection visit, data collectors will be asked to guess whether participants had received the active or control intervention at the visit. These data will provide some measurement of the success of masking.

7 STUDY INTERVENTION/EXPERIMENTAL MANIPULATION DISCONTINUATION AND PARTICIPANT DISCONTINUATION/WITHDRAWAL

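### Arm effects are tested at 5% on eight randomised PCPs with no small-sample reference named; for between-PCP contrasts a z test would run at about 9–10%

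*Combined protocol and SAP*

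**What the plan says.** Section 9.4.2 sets the design: "This is a group-randomized trial in which the primary care providers (PCPs) will be randomized within sites to the active and control conditions". It then places the analysis one level lower: "Outcomes will be analyzed at the level of the early adolescent and/or caregiver". The method is "Intervention effects will be assessed using linear mixed models (LMM) or generalized linear mixed models (GLMM) for continuous and categorical outcomes, respectively", and "All hypothesis tests will be two-sided at level" 0.05. Section 4.1 repeats the method and the level.

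Section 9.2 gives the size: "With a sample size of 10 patients/PCP and 4 PCPs in each intervention arm", with 20% attrition and an ICC of 0.2 for PCPs. Section 6.3 agrees on four per arm, for example "two physicians and two NPs randomized to control".

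The model in 9.4.2 has a random intercept for PCP and one for patient. The only test it names is H0: β3 = 0, where β3 is the coefficient of a pre/post indicator. Neither 4.1 nor 9.4 states REML or ML, a reference distribution, a degrees-of-freedom method or how intervals are formed.

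Two further facts matter. Hypothesis 2 includes higher perceived shared decision-making, and the synopsis and the section 8 schedule have trial participants complete SDM-Q-9 only once, immediately after the visit. The number of PCPs is also inconsistent. It is eight in most places, but the synopsis text on inclusion of women refers to 16 clinicians. The randomisation text in 4.1 can be read as eight per condition, although it ends with a total of eight.

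**The concern.** Arm varies only between PCPs. When an outcome has no pre-visit value, the arm comparison is a comparison of four PCP averages with four others, however many dyads each PCP enrols. The PCP variance must then be estimated from eight units, and a normal cut-off treats that estimate as known. Many mixed-model procedures allow either a normal or a small-sample reference, and with eight clusters the choice matters.

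Section 9.4.2 says the secondary measures will inform a future trial. A chance difference in SDM-Q-9 declared significant, or an interval that is too short, would feed directly into that trial's design.

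**Working it through.** **Inputs.** Level 0.05 two-sided (9.4.2); four PCPs per arm, 10 dyads per PCP, 20% attrition so m = 8 completers, ICC 0.2, repeated-measures correlation 0.8 (9.2). Total variance is set to 1.

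**Plan's own figure.** The figure at issue is the 5% level. It is recovered if the PCP variance is known: P(|Z| > 1.96) = 0.05. The 80% power in 9.2 is not used here. It could not be reproduced from any between-arm contrast (0.06–0.07 for a post-visit mean with ICC 0.2), which is a separate matter.

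**Variance of a post-only arm difference.** Var = (2/4) × [0.2 + 0.8/8] = 0.5 × 0.3 = 0.15, so SE = 0.387. Two-thirds of the bracket (0.2/0.3) is PCP variance.

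**Reference distribution.** In a balanced design this variance is estimated from PCP means within arms, on 8 − 2 = 6 df.
- Size of a z test: P(|t6| > 1.96) = 0.0977, and 0.0977/0.05 = 1.95.
- Coverage of a z-based 95% interval: 1 − 0.0977 = 0.902.
- Width relative to the correct interval: 1.960/2.447 = 0.80. Conversely 2.447/1.960 = 1.25.

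**Simulation at ICC 0.2.** A single post-visit continuous outcome with 8–10 dyads per PCP (40,000 balanced trials) gave 9.1–9.4% with REML and z, and 5.0–5.1% with t on 6 df. ML with z gave 12.7–13.1%. A logistic GLMM with Wald z (latent ICC 0.2, event rate 30–50%, 1,500 trials per setting, two separate runs) gave 7.9–11.3%; with t on 6 df it gave 2.7–4.9%. The Monte Carlo standard error of the GLMM rates near 10% is √(0.1 × 0.9/1,500) = 0.8 percentage points.

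**Sensitivity of the z-test size for a between-PCP contrast.**

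| Setting | Size |
|---|---|
| 8 PCPs, arm only (6 df) | 9.8% |
| also adjusting for provider type (5 df) | 10.7% |
| also for two sites (4 df) | 12.2% |
| 16 PCPs (14 df) | 7.0% |
| 8 PCPs, ICC 0.05, REML held non-negative (simulated) | 6.8% |
| 8 PCPs, ICC 0.01, REML held non-negative (simulated) | 4.7% |

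**β3 as printed.** The PCP and patient intercepts cancel from a pre/post contrast. Simulated size of the z test with no change in either arm is 4.9%, so the degrees-of-freedom problem is absent. The separate fault is that β3 does not compare the arms: an equal improvement of 0.30 SD in both is significant in 84% of trials.

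**If the tested term becomes arm-by-post.** Size now depends on how much PCPs differ in change over time. The documents give no value, so the variances below are assumed, as shares of total variance (15,000 trials each, 8 patients per PCP, 1 pre and 3 post).

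| PCP-by-period variance | Random intercepts only, z | PCP-by-period term, z | PCP-by-period term, t6 |
|---|---|---|---|
| 0 | 5.2% | 4.3% | 1.4% |
| 0.02 | 11.5% | 6.5% | 2.5% |
| 0.05 | 21.4% | 8.9% | 4.2% |
| 0.10 | 30.8% | 9.6% | 4.6% |

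The missing variance term does the larger damage. The t reference completes the repair once that term is in the model.

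**The case against.** A reader might infer that all planned tests, including the primary ACQ test, run at twice the stated level. The documents do not support that. The one named test is β3, which has about its nominal size under its own null. Repeated outcomes such as dichotomised MARS-A have a baseline and three follow-ups, so they fall under the same test. Exacerbation is scheduled at follow-up only, but its description reaches back to oral steroid use in the year before the intervention, so it is not clearly post-only. The clear cases are SDM-Q-9 and the debriefing survey.

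A reader might also infer that the plan has chosen Wald z tests or ML. It has not; it is silent, and software defaults could supply a t reference. That objection stands, and the point is therefore an open risk.

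Nor do the documents settle whether a re-randomisation test could reach 0.05. Stratifying eight PCPs by provider type alone gives 6 × 6 = 36 allocations and a smallest two-sided p of 2/36 = 0.056. But 9.4.2 randomises within sites, and 4.1 and 6.3 randomise all eligible clinicians before enrolling from the list. The reference set is thus not defined well enough for that count.

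Finally, this is a feasibility pilot with exploratory secondary outcomes. That lowers the stakes. It does not remove the plan's claim to test them at 5%.

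**Conclusion.** The omission is real and its effect is material for arm comparisons between PCPs. With eight PCPs and ICC 0.2, a z reference gives about 9–10% false positives and 95% intervals with about 90% coverage. This rests on three assumptions: that a large-sample reference would be used, that eight PCPs are analysed, and that the ICC is near the plan's 0.2. Inflation falls to about 6–7% at an ICC of 0.05 and vanishes at 0.01 when the variance estimate is held non-negative. It is 7.0% with 16 PCPs. The GLMM result is simulation-based and covers event rates of 30–50% only. For ACQ, no degrees-of-freedom rule is enough until the tested term compares the arms.

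**What to change.** In 9.4.2 and 4.1:

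- Fit LMMs by REML with Kenward-Roger (or Satterthwaite) degrees of freedom.
- For GLMM arm effects, use a t reference with between-PCP df equal to the number of PCPs analysed minus the number of PCP-level fixed parameters: 6 with eight PCPs and arm only, 5 if provider type is adjusted for. Stated as a rule, this adapts if PCPs are replaced.
- Use the same reference for all 95% intervals.
- For ACQ and other repeated outcomes, first redefine the tested term as an arm-by-post contrast with a PCP-by-period random effect, then apply the rule.
- Reconcile the PCP count (8 versus 16).

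The cost is wording and a software option, with no new data. Intervals for between-PCP contrasts become about 25% wider than z-based ones. The tests are somewhat conservative when between-PCP variance is small: GLMM size was as low as 2.7%, and the arm-by-post t test had size 1.4% when PCPs did not differ in change over time.
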